- x. Ethesioneuroblastoma (At relapse after standard of care therapy and/or non- responsive/progressive to accepted curative chemotherapy).
- xi. Neuroendocrine tumors (At relapse after standard of care therapy and/or non- responsive/progressive to accepted curative chemotherapy).
- xii. Desmoplastic small round cell tumor (At relapse after standard of care therapy and/or non- responsive/progressive to accepted curative chemotherapy).
- xiii. Melanoma (At relapse after standard of care therapy and/or non- responsive/progressive to accepted curative chemotherapy).

2. Subjects must be age \geq 12 months at enrollment
3. Subjects must be age \leq 21 years at initial diagnosis
4. Subjects must have measurable disease as defined by RESIST v1.1 at the time of biopsy and tumor must be accessible for biopsy. Tumor samples submitted for analysis must contain $>50\%$ viable tumor tissue to qualify. In addition, subjects with disease confined to the bone marrow are eligible to enroll if the degree of marrow involvement is expected to be $>50\%$.
Note: Subjects who are expected to have no evidence of disease after surgical removal of their tumor are still eligible for this trial if their disease would normally require adjuvant chemotherapy treatment after surgery despite NED status.
5. Current disease state must be one for which there is currently no known effective therapy
6. Specimens will be obtained only in a non-significant risk manner and not solely for the purpose of investigational testing.
7. Lansky or Karnofsky Score must be ≥ 50
8. Subjects without bone marrow metastases must have an ANC $> 750/\mu\text{l}$ to begin treatment.
9. Subjects with CNS disease currently taking steroids must have been on a stable dose of steroids for 2 weeks prior to their biopsy and must not have progressive hydrocephalus at enrollment.
10. Adequate liver function must be demonstrated, defined as:
 - a. Total bilirubin $\leq 1.5 \times$ upper limit of normal (ULN) for age AND
 - b. ALT (SGPT) $< 10 \times$ upper limit of normal (ULN) for age
11. A negative serum pregnancy test is required for female participants of child bearing potential (≥ 13 years of age or after onset of menses)

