5.3.6 Reevaluation during Subsequent (Maintenance) Cycles

Subjects will be assessed for disease at the end of cycle 2 and every other cycle or every 8 weeks*, whichever occurs first, with the following (timing should be during the last week of the cycle):

1. CT or MRI of measurable disease sites (same scans as done at study entry);
2. MIBG/PET scan (if indicated for tumor type). Other imaging appropriate for tumor type may also be considered;
3. Any subject with suspected bone marrow disease and with positive bone marrow disease at study entry: Bone marrow aspirate and biopsy.

*After Cycle 6, reevaluations procedures in section 5.3.6 may be done per institutional standard.

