- **Progressive Disease (PD):** At least a 20% increase in the sum of the disease measurements for measurable lesions, taking as reference the smallest disease measurement recorded since the start of treatment (nadir), and minimum 5 mm increase over the nadir or the appearance of one or more new lesions.

Response Criteria for Subjects with Bone Marrow Disease:

- Those subjects with morphologic evidence of disease by routine H and E staining (NSE staining only is not evaluable) will be evaluable to assess bone marrow response.
- **Complete response:** No tumor cells detectable by routine morphology on two consecutive bilateral bone marrow aspirates and biopsies done at least three weeks apart after study entry.
- **Progressive disease:** Tumor seen on morphology on two consecutive bone marrows done at least three weeks apart in subjects who had NO tumor in bone marrow at study entry. (Note: Subject may be declared as progressive disease in bone marrow after only one diagnostic bone marrow at the discretion of the treating physician after discussion with the study chair.)
- **Stable disease:** Persistence of an amount of tumor in the bone marrow by morphology that does not meet criteria for either complete response or progressive disease.

Response Criteria for Subjects with MIBG or PET Positive Lesions

- Subjects who have a positive MIBG or PET scan at the start of therapy will be evaluable for MIBG or PET response. All MIBG's and PET scans will be performed at the research institution and then centrally reviewed.
- **Complete response** = complete resolution of all positive lesions
- **Partial response** = resolution of at least one positive lesion, with persistence of other MIBG positive lesions.
- **Stable disease** = no change in scan in number of positive lesions (includes subjects who have same number of positive lesions but decreased intensity)
- **Progressive disease** = Development of new positive lesions

The intensity of MIBG uptake is not to be considered in the above institutional evaluation.

Duration of response:

Duration of response is defined as the period of time from when measurement criteria are met for complete response (CR) or partial response (PR), whichever is first recorded, until the first date that recurrent or progressive disease (PD) is objectively documented (taking as reference for PD the smallest measurements recorded since the treatment started).

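### No marrow progression rule is written for subjects with marrow tumor at entry, so worsening marrow disease is scored as stable and PFS is biased upward

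*Combined protocol and SAP*

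**What the plan says.** All references are to the combined protocol and SAP.

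- **Eligibility.** Under inclusion criterion 4 (Section 4.1), "subjects with disease confined to the bone marrow are eligible to enroll" if expected involvement exceeds 50%. Section 5.2 lets a marrow core serve as the primary sample.
- **Who is evaluable for marrow response (Section 7.3).** "Those subjects with morphologic evidence of disease by routine H and E staining".
- **Marrow progression (Section 7.3).** Tumor on two consecutive marrows at least three weeks apart, "in subjects who had NO tumor in bone marrow at study entry". A Note, which also requires that the study chair be consulted, adds: "Subject may be declared as progressive disease in bone marrow after only one diagnostic bone marrow at the discretion of the treating physician".
- **Marrow stable disease (Section 7.3).** "Persistence of an amount of tumor in the bone marrow by morphology that does not meet criteria for either complete response or progressive disease".
- **Marrow complete response (Section 7.3).** No tumor on two consecutive bilateral examinations at least three weeks apart. There is no marrow partial response.
- **Repeat marrows (Section 5.3.6).** "Any subject with suspected bone marrow disease and with positive bone marrow disease at study entry: Bone marrow aspirate and biopsy".
- **PFS (end of Section 7.3).** Time from the first study drug until the progression criteria are met. Death is not named as an event.
- **Use of PFS.** It is a secondary objective (Section 2.2), is analysed by Kaplan-Meier and Cox methods (Section 12.4), and is compared between the two cohorts of 100 (Section 8).

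**The concern.** The evaluability line and the progression line describe opposite groups. If evaluability is judged at entry, the subjects evaluable for marrow response have marrow tumor, while those who can meet written marrow progression had none. A subject with marrow tumor at entry is left with two categories, complete response and stable disease, and the second has no ceiling.

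The trial deliberately enrolls subjects for whom the marrow is the only known disease site. Subjects with marrow plus soft-tissue disease are affected too, whenever the marrow is the site that worsens. PFS depends entirely on the progression criteria, so it inherits the gap. Because death is not named, a missed marrow progression would not clearly be caught later as a death. Stable disease also counts towards clinical response when tumor markers fall by at least 50%, so a worsening marrow need not prevent that classification.

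**Working it through.** **Step 1. Apply Section 7.3 as written.** The percentages in the third row are an invented example.

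| Marrow at entry | Finding on study | Category |
|---|---|---|
| Negative | Tumor on two marrows, three or more weeks apart | Progression |
| Positive | Clear on two examinations, three or more weeks apart | Complete response |
| Positive, 55% tumor | 95% tumor | Stable disease |
| Positive, then cleared | Tumor returns | Not progression: the entry condition fails |

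The last two rows are the gap. Section 5.3.6 obtains marrows in entry-positive subjects, so the evidence would be collected but could not be scored as progression.

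**Step 2. Direction.** Leaving out true progressions removes PFS events or delays them. The bias in estimated PFS is upward.

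**Step 3. Size.** The plan states no PFS figure to reproduce. Its only design figures are those of the two-stage feasibility rule, which does not use progression. With limits of 5/9 and 10/16, the exact binomial gives stage 1 stopping probabilities of 0.746 at 50% and 0.166 at 75%, as Section 8 states.

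The documents do not say how many subjects are marrow-positive or marrow-confined. I therefore assume a share f of subjects whose progressions all go uncounted, with exponential PFS of true median m and the same hazard in everyone. There are two ways to handle the affected subjects:

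- *Censored at the uncounted progression.* The counted hazard is (1 − f) times the true one, so the median is multiplied by 1/(1 − f).
- *Kept on study as stable.* Solve (1 − f)·2^(−t/m) + f = 0.5, which gives t/m = log2[(1 − f)/(0.5 − f)].

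| Assumed f | Censored | Kept as stable |
|---|---|---|
| 5% | 1/0.95 = 1.05 | log2(0.95/0.45) = 1.08 |
| 10% | 1/0.90 = 1.11 | log2(0.90/0.40) = 1.17 |
| 20% | 1/0.80 = 1.25 | log2(0.80/0.30) = 1.42 |

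If f were 2%, the multipliers would be 1.02 and 1.03.

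**The case against.** **The Note.** It allows marrow progression to be declared at the physician's discretion and does not repeat the clean-marrow condition, so it might be read as covering everyone. Its wording, however, concerns one marrow in place of two. The natural reading relaxes confirmation only. Read broadly, it would still give no criterion for an entry-positive marrow. The ambiguity does rule out saying that such a subject can never be declared progressive in marrow.

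**Other routes to progression.** New CT/MRI lesions, and new MIBG or PET lesions, count as progression. A reader might infer that PFS among marrow-only subjects stays near 100%. The documents do not support that: these subjects can progress outside the marrow, and they can leave therapy or study under Section 11.

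**Duration of response.** A reader might infer that this is overstated too, or that a marrow complete response never ends. Neither follows. Section 7.3 ends duration of response at recurrence as well as progression, and has serial marrows reviewed in responders. What stays undefined is whether such a recurrence is also a PFS event.

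**The schedule.** A reader might infer from Section 5.3.6 that no scheduled marrow can yield marrow progression. That is too strong. The sentence can be read as naming two groups, and Section 9.3.2 recommends aspirates after cycle 2 and every two cycles thereafter in neuroblastoma or suspected marrow disease, whatever the entry status. Those are optional research samples with no stated morphology reading, so they do not close the gap.

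**Comparison with earlier regimens.** A tilt towards the study regimen is plausible, but the documents do not say how earlier PFS intervals were scored.

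**Importance.** PFS is secondary, the feasibility criteria are reported as met in all strata, and the affected share may be small. This stands and lowers the priority of the point.

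**Conclusion.** The gap holds on the text. It is a stated rule that gives a wrong score, not merely missing detail: followed literally, it classifies clear marrow worsening in an eligible group as stable disease, and it does not count marrow relapse after clearing as progression. PFS is biased upward.

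The size cannot be determined from the documents. The multipliers of 1.05 to 1.25 (censored) and 1.08 to 1.42 (kept as stable) rest on an assumed share of 5% to 20%, exponential PFS with a common hazard, and every progression in the affected subjects going uncounted. They show scale and are not an estimate for this trial. The conclusion also assumes the narrow reading of the Note.

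This should be fixed before PFS is analysed. It does not threaten the primary objective.

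**What to change.** For endpoint scoring of PFS only:

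1. In Section 7.3, count as progression, for subjects with marrow tumor at entry, (a) marrow recurrence after documented clearing and (b) a pre-specified increase in marrow tumor. The increase cannot be defined as a doubling for subjects above 50%, since 2 × 50% is already 100%.
2. Limit marrow stable disease to changes short of that increase.
3. State whether the Note lifts the clean-marrow condition or only the two-marrow confirmation.
4. Reconcile Section 7.3 with Sections 4.1, 5.3.6 and 9.3.2. Also reconcile it with Section 11.1, where progressive disease is a reason to leave therapy, and say explicitly how the scoring definition relates to that criterion. This point does not propose when treatment should stop and does not ask for additional marrow procedures.
5. Where percent marrow tumor was not recorded in the first cohort, report PFS for marrow-positive subjects separately.

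The cost is a few sentences in Section 7.3, and a usable percent-tumor reading from marrows already taken in entry-positive subjects, where Section 7.3 now asks only for morphology. Reported PFS becomes slightly less favourable.

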	
targets and will be performed after cycle 2, then after every other cycle.
 
 • A subject will be defined as a responder if CR/PR is observed at any time of the treatment • Clinical response will be seen if stable disease and decrease in tumor markers by $\geq 50\%$ or CR of bone marrow. • Time to progression, defined as the period from the start of the treatment until the criteria for progression are met taking as reference the screening measurements • Comparisons of ORR and PFS for the first and second cohorts of 100 patients (i.e., those who enroll prior to versus after the implementation of Amendment 3.0, respectively) will be performed. 
Safety Measures: Secondary objectives
 
 • Safety analysis will be conducted on all subjects who have received at least one dose of therapy, and will include the frequency of all reported adverse events and laboratory abnormalities as well as frequency of dose interruptions, dose reductions and treatment discontinuation.
STATISTICS/SAMPLE SIZE ESTIMATE	
200 evaluable subjects
 
Patients who enroll following implementation of Amendment 3.0 (second cohort of 100 patients) will have their tumor biopsies analyzed using an updated Drug Prediction Report (Appendix III). Overall Response Rate (ORR) and Progression Free Survival (PFS) for this group will be compared to those of the first 100 patients who received treatment based upon the original Drug Prediciton Report and Pharmacopeia Library.

TABLE OF PROCEDURES AND ASSESSMENTS

Procedure	Screening	Cycle 1 Day 1	Cycle 1 Day 8	Cycle 1 Day 15	Cycle 1 Day 22 (if applicable)	Subsequent Cycles Day 1	Off Therapy/ 30 Day Follow-up
Informed consent	X						
Demographics	X						
Medical history	X	X	X	X	X	X	
Baseline Symptom Form	X	X					
Concurrent meds	X	X				X	X
Physical exam	X	X	X	X	X	X	X
Vital signs	X	X	X	X	X	X	X
Height	X	X				X	
Weight	X	X				X	X
Karnofsky or Lansky play score	X	X		X		X	X
CBC w/diff,	X	X	X	X	X	X	X
Serum chemistry *	X	X		X		X	X
Tumor Markers **	X	X				X	X
Adverse events			X	X	X	X	X
Surgical resection &/or diagnostic biopsy	X						
MRI or CT***	X						
MIBG/PET ***	X						
Bone Marrow (any subject suspected to have BM disease) ^	X						
B-HCG	X						
EKG (as indicated)		X					

* Serum electrolytes, BUN, Creatinine, Bilirubin, ALT, AST

**LDH and/or Specific Tumor Markers for defined disease (if available)

***Type of scan as indicated for disease type

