7.3 Response Criteria

Overall response rate (ORR) in subjects with radiologically assessable disease will be determined by CT or MRI by cross-sectional imaging, MIBG/PET scans, and/or bone marrow assessment.

Response Assessment: Each subject will be classified according to their “best response” for the purposes of analysis of treatment effect. Best response is determined from the sequence of the objective statuses described below.

Response Criteria for Subjects with Solid Tumors: This study will use the (RECIST) Response Evaluation Criteria in Solid Tumor (version 1.1) from the NCI[44]. Key points are that a maximum of 5 target lesions are identified and that changes in the *largest* diameter (uni-dimensional measurement) of the tumor lesions are used in the RECIST v1.1 criteria.

- **Measurable disease:** The presence of at least one lesion that can be accurately measured in at least one dimension with the longest diameter at least 10 mm (CT scan slice thickness no greater than 5 mm). The investigator will identify up to 5 measurable lesions to be followed for response. Previously irradiated lesions must demonstrate clear evidence of progression to be considered measurable.
- Serial measurements of lesions are to be done with CT or MRI, using the same method of assessment is to be used to characterize each identified and reported lesion at baseline and during follow-up.

- Quantification of Disease Burden The sum of the longest diameter (LD) for all target lesions will be calculated and reported as the disease measurement.
- **Complete Response (CR):** Disappearance of all target and non-target lesions.
- **Very Good Partial Response (VGPR):** Greater than 90% decrease of the disease measurement for CT/MRI lesions, taking as reference the disease measurement done to confirm measurable disease at study entry. Non-target CT/MRI lesions stable to smaller in size.
- **Partial Response (PR):** At least a 30% decrease in the disease measurement, taking as reference the disease measurement done to confirm measurable disease at study enrollment. No new lesions or progression of any non-target measurable lesion.
- **Stable Disease (SD):** Neither sufficient decrease to qualify for PR or sufficient increase to qualify for PD from study entry.

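### MIBG/PET partial response needs one lesion to resolve out of any number and does not exclude new lesions, so ORR should be shown with and without responses that rest on MIBG/PET alone

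*Combined protocol and SAP*

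**What the plan says.** Section 7.3 sets separate criteria for CT/MRI, bone marrow and MIBG/PET.

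- **MIBG/PET.** PR is "resolution of at least one positive lesion, with persistence of other MIBG positive lesions". Stable disease is "no change in scan in number of positive lesions", and lesions that only fade count as stable. Progression is "Development of new positive lesions". The section adds: "The intensity of MIBG uptake is not to be considered in the above institutional evaluation". These scans are to be centrally reviewed.
- **CT/MRI.** PR is "At least a 30% decrease in the disease measurement", which is the sum of longest diameters, with the further condition "No new lesions or progression of any non-target measurable lesion". For this method "a maximum of 5 target lesions are identified". No cap on lesions is given for MIBG/PET.
- **Marrow.** Complete response needs two consecutive negative assessments at least three weeks apart. No repeat scan is asked for on MIBG/PET.

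ORR draws on CT/MRI, MIBG/PET and/or marrow (section 7.3). The synopsis, under Criteria for Evaluation, states: "A subject will be defined as a responder if CR/PR is observed at any time of the treatment". Section 12.4 reports response rates with exact 95% confidence intervals. The synopsis and section 8 also plan to compare ORR between the first 100 patients and those enrolled after Amendment 3.0.

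**The concern.** The MIBG/PET threshold is an absolute count of one. Because stable disease requires an unchanged count, losing a single lesion out of any number moves a subject out of stable disease and into PR. Each lesion is read as present or absent, so the more lesions a subject has, the more chances there are for one to go unseen on a scan without real change. One such reading can then stand as best response.

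The definition also overlaps with progression. A scan on which one lesion has cleared and another has appeared meets both categories, and nothing in section 7.3 says which prevails.

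ORR is a secondary endpoint, but it is the plan's named measure of activity and one of two measures used to compare the cohorts before and after Amendment 3.0. If MIBG/PET use or lesion burden differs between those cohorts, ORR could shift for reasons unrelated to the updated drug report.

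**Working it through.** The plan gives no sample size, power or expected value for ORR, so there is no figure of its own to reproduce. Its calculated design figures concern feasibility and play no part here.

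**1. Smallest change that qualifies as PR.** With k positive lesions at baseline, it is 1/k.

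| k | 2 | 3 | 4 | 5 | 10 | 20 |
|---|---|---|---|---|---|---|
| 1/k | 50% | 33% | 25% | 20% | 10% | 5% |

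At 2 or 3 lesions this is no looser than 30%. From 4 upward it is looser. The documents give no lesion counts, so the values of k are illustrations.

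**2. Chance of a false PR on one scan.** Let e be the chance that a persisting lesion is read as resolved, with errors independent between lesions. Both are assumptions; the documents give no value for e. In an unchanged subject, the chance that at least one lesion is read as resolved is 1 − (1 − e)^k. For example, 1 − 0.98^10 = 0.183.

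| e | k = 5 | k = 10 | k = 20 |
|---|---|---|---|
| 1% | 4.9% | 9.6% | 18.2% |
| 2% | 9.6% | 18.3% | 33.2% |
| 5% | 22.6% | 40.1% | 64.2% |

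The chance that every lesion is misread, which would be a complete response, is negligible at these k. For any e above zero, the false-PR chance rises with k.

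**3. Misread new lesions.** A lesion wrongly read as new would make the scan progressive. If 10% to 20% of scans had one, independently of the other errors, the figures above would be multiplied by 0.9 to 0.8. At e = 2% and k = 10, 18.3% becomes 16.5% to 14.6%. This applies only if progression overrides PR, which the text does not say.

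**4. A proportional rule for comparison.** Require at least 30% of lesions to resolve: 2 of 5, 3 of 10 or 6 of 20. At e = 2% the binomial upper tails are 0.4%, 0.09% and below 0.01%. At 2 or 3 lesions, one lesion is already at least 30%, so the two rules coincide. There, at e = 5%, the chance stays at 1 − 0.95² = 9.8% and 1 − 0.95³ = 14.3%.

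**5. Effect on ORR, illustration only.** Assume a true ORR of 10%, a share s of subjects evaluable by MIBG/PET, a false-PR chance of 18%, and that an MIBG/PET PR alone makes a responder. Observed ORR is 0.10 + 0.90 × s × 0.18:

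- s = 25%: 0.10 + 0.0405 = 14%
- s = 50%: 0.10 + 0.081 = 18%

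None of these inputs is in the documents.

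**The case against.** The strongest reply is that the rule is not simply lax. A lesion must clear completely, and fading is stable disease, so in that respect it is stricter than a 30% shrinkage. A lesion count and a sum of diameters are different scales, so their percentages cannot be set directly against each other. That stands.

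Safeguards also exist. Scans are centrally reviewed, which should lower e, and section 7.3 has serial marrow, biopsy and urinary catecholamine results reviewed for responders. Neither sets a minimum change or requires a second scan. A perfect reader would still have to call the loss of one lesion in ten a PR.

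A reader might infer that a 5% change counts as an objective response. That needs 20 baseline lesions, a number the documents do not give. A reader might also infer that every MIBG/PET PR is a responder and that ORR is therefore materially inflated. The documents do not support that either. Most subjects must have measurable disease under inclusion criterion 4, MIBG/PET is done only where indicated for the tumor type, and the plan does not say how an MIBG/PET PR combines with CT/MRI stable disease.

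Finally, it is tempting to replace the threshold with 30% of lesions. That borrows a fraction from another scale, changes the definition after 100 subjects have enrolled in an open-label study, and leaves false PRs at 2 or 3 lesions untouched. It is debatable as a primary rule and better used as a sensitivity analysis.

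**Conclusion.** The point holds in a limited form. MIBG/PET PR has no minimum proportion, no repeat scan and no exclusion of new lesions. The overlap between PR and progression follows from the text alone. The proportional looseness begins at four lesions.

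The false-PR chance per scan, 5% to 18% at e = 1% and 10% to 33% at e = 2% for 5 to 20 lesions, rests on an assumed e, independence between lesions and no allowance for misread new lesions. The direction does not depend on e; the size does.

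The effect on trial ORR is unknown. ORR is secondary, has no decision threshold, and both cohorts share the same rule. This is therefore an inexpensive improvement to reporting and does not invalidate the activity analysis.

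**What to change.** - **Section 7.3.** Keep the one-lesion rule as the primary MIBG/PET definition, for continuity with the first 100 subjects. Add the condition that no new lesion is present, so that PR and progression cannot both apply. The progression definition stays as it is.
- **Section 12.4.** Report ORR, including the comparison of the two cohorts, with and without responses that rest on MIBG/PET alone. This also shows how much depends on the unstated rule for combining modalities.
- **Sensitivity analysis.** Repeat ORR requiring a proportional fall in the number of positive lesions, for example at least 30%, where lesion counts are recorded.

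The cost is one added condition and some extra analysis of scans already collected. The documents do not say whether per-lesion counts were recorded, so the last analysis may be incomplete. ORR may come out lower in the sensitivity analyses, and any subject previously classed as PR with a new lesion on the same scan would need to be reclassified.

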ESTIMATED NUMBER OF PATIENTS/GEOGRAPHIC REGIONS	
200 evaluable (220 total) relapsed/refractory pediatric cancer patients. Additional patients may enroll through compassionate access if no other treatment options are available.
 
Patients will enroll at:
 
Arnold Palmer Children's Hospital, FL St. Louis University/Cardinal Glennon Children's Medical Center, MO Helen DeVos Children's Hospital, MI Levine Children's Hospital, NC Connecticut Children's Medical Center, CT Children's Mercy Hospital, Kansas City MO Rady Children's Hospital of San Diego, CA Medical University of South Carolina, SC Monroe Carrell Jr. Children's Hospital at Vanderbilt, TN Kapiolani Medical Center for Women and Children, HI Dell Children's Hospital, TX Texas Children's Hospital, Baylor College of Medicine, TX Primary Children's Hospital, UT Children's Hospital and Clinics of Minnesota, MN Penn State Milton S. Hershey Medical Center and Children's Hospital, Hershey, PA Arkansas Children's Hospital – Little Rock, AR 
International Sites
 American University of Beirut Medical Center, Lebanon La Timone; Marseille, France

LENGTH OF STUDY	Accrual to this study is estimated to be approximately 3-4 years.
STUDY ASSESSMENTS	Refer to Table of Assessments for timing of study procedures.
CRITERIA FOR EVALUATION	
Feasibility Measures: Primary objective: The definition of feasibility for this study will include: “Enrollment onto study, genomic profile, analysis and report generation completed, tumor board held with treatment decision, treatment review completed, start of treatment, and completion of 1 cycle of therapy.”
 
Efficacy Measures: Secondary objectives Response: To determine the overall response rate (ORR) by the presence of radiologically assessable disease by cross-sectional CT or MRI imaging and/or by MIBG or PET scans.
 
 ◆ Duration of response, defined as the period of time from when measurement criteria are met for complete response (CR) or partial response (PR), whichever is first recorded, until the first date that recurrent or progressive disease (PD) is objectively documented (taking as reference for PD the smallest measurements recorded since the treatment started) ◆ The assessment of response will include the initial measurable

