Please note that many of the drugs that will be considered for proposed individualized combination therapy in this protocol are not considered cytotoxic agents and therefore will not have previously been specifically tested as part of conventional antineoplastic protocols. Examples of these medications may include anti-seizure or anti-cholesterol agents. These non-cytotoxic agents will be used at standard doses based on recommendations of an experienced pediatric pharmacist and described pharmacy programs that are used to evaluate potential interactions and combination dosing for all medications. The final treatment regimen will be subjected to a 12 hour in depth review and evaluation for safety and then be signed off by one of the protocol pharmacists. The treatment memo will then be discussed with the subject and their parents (if the subject is < 18 years of age).

3.2 Additional Biopsies:

Subjects that are having additional biopsies done as standard of care during the course of the study, when deemed appropriate by study PI, may complete the study process again and have new reports generated on the latest tumor. A new tumor board discussion will occur utilizing all rules of this protocol and the new reports. The subject may then change treatment regimens based on the decision of the tumor board. All protocol requirements and specifications will be followed as if it were a new biopsy.

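### MIBG/PET partial response does not exclude new lesions and no rule gives progression precedence, so one scan can make a subject both an ORR responder and a PFS failure

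*Combined protocol and SAP*

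**What the plan says.** Section 7.3 gives separate response criteria for each way of measuring disease.

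- **MIBG or PET, partial response:** "resolution of at least one positive lesion, with persistence of other MIBG positive lesions".
- **MIBG or PET, progressive disease:** "Development of new positive lesions".
- **CT or MRI, partial response:** a decrease of at least 30% in the disease measurement, with the added condition "No new lesions or progression of any non-target measurable lesion".

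On combining these, Section 7.3 says that ORR "will be determined by CT or MRI by cross-sectional imaging, MIBG/PET scans, and/or bone marrow assessment". The synopsis (Criteria for Evaluation) says that it is assessed "by cross-sectional CT or MRI imaging and/or by MIBG or PET scans". On reducing a subject's course to one outcome, Section 7.3 says "Best response is determined from the sequence of the objective statuses described below", and the synopsis says "A subject will be defined as a responder if CR/PR is observed at any time of the treatment".

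Two other places bear on the point. Section 3.2 lets a subject who has a further standard-of-care biopsy go through the profiling process again: "The subject may then change treatment regimens based on the decision of the tumor board". Section 11.1 lists progressive disease among the reasons for removing a subject from study therapy.

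**The concern.** Response categories should be mutually exclusive at a given time point, or the plan should say which one prevails. Here the MIBG/PET partial response and progression definitions overlap. The safeguard that would prevent this is written for CT/MRI in the same section but is missing for MIBG/PET.

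The two rules that could settle the conflict later are also silent. Nothing says what status a time point has when the modalities disagree, and nothing says that responses stop counting at first progression.

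At stake is the consistency of the secondary efficacy results. ORR and PFS are both secondary measures, and both are to be compared between the subjects enrolled before and after Amendment 3.0 (synopsis and Section 8). If the same scan can be a success for one and a failure for the other, two analysts working from the same data can report different response rates, and both can claim to follow the protocol.

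**Working it through.** The documents give no target, power or expected value for ORR, so there is no planned figure to reproduce. The check is one of definitions.

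**Step 1: one MIBG/PET scan, all patterns.** Classify baseline lesions as resolved or persisting, and note whether a new lesion is present. Applying the Section 7.3 definitions literally gives:

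| Resolved | Persisting | New | Categories met |
|---|---|---|---|
| none | at least 1 | none | SD |
| none | at least 1 | at least 1 | PD |
| all | none | none | CR |
| at least 1 | at least 1 | none | PR |
| at least 1 | at least 1 | at least 1 | **PR and PD** (also SD if the lesion count is unchanged) |
| all | none | at least 1 | PD (also CR if only baseline lesions are meant; also SD if the count is unchanged) |

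Without new lesions, each pattern falls into one category. Every overlap needs a new lesion, which is the condition that CT/MRI partial response excludes.

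**Step 2: look for a rule that resolves the overlap.**

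- Precedence of PD over PR on the same scan: none stated.
- One overall status across CT/MRI, MIBG/PET and marrow: none stated. The modalities are only listed together.
- Cut-off at first progression: neither the best-response sentence nor the responder sentence contains one.

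**Step 3: follow the PR-and-PD scan through the endpoints.**

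- ORR: partial response has been observed during treatment, so the responder rule is met.
- PFS: Section 7.3 measures from the first day of study drug until the progression criteria are met. They are met on this scan, so the subject has an event.
- Duration of response: this runs from the date on which CR or PR is first met to the first documented PD. Both dates are the date of this scan, so the duration is zero. If the first PD came before the PR, the same subtraction would be negative, so the duration is in effect undefined.

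**Step 4: size.** The number of subjects affected depends on how many have MIBG or PET disease, how often a resolved and a new lesion appear together, and how readers settle the conflict. The documents give none of these. What can be stated is the unit of error, taking all planned subjects as the denominator: one misclassified subject is 1/100 = 1 percentage point in a cohort of 100, and 1/50 = 2 points in the neuroblastoma or brain tumor stratum.

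To compare this with sampling error, take assumed counts in a cohort of 100 (exact 95% intervals). The starting values are the ends of the 10% to 35% range that Section 1.2 cites for relapsed neuroblastoma studies.

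| Correct responders | None added | 5 added | 10 added |
|---|---|---|---|
| 10 | 10% (4.9 to 17.6) | 15% (8.6 to 23.5) | 20% (12.7 to 29.2) |
| 35 | 35% (25.7 to 45.2) | 40% (30.3 to 50.3) | 45% (35.0 to 55.3) |

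This shows sensitivity only. The 0, 5 and 10 are not estimates of how many subjects would be misclassified.

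**The case against.** The strongest reply is that a sensible reader would apply progression first. PD is defined separately, each subject gets one best response from a sequence of statuses, and MIBG and PET scans are centrally reviewed. Section 7.3 also says that marrow results and urinary catecholamines of responding subjects will be reviewed to confirm response or absence of progression, and it adopts RECIST 1.1 for solid tumors. These are real safeguards, and the marrow review partly covers one conflict. They do not close the gap. Central reviewers apply the same overlapping definitions, the review of responders does not address conflicts between imaging methods, and the text does not extend RECIST to MIBG/PET or to combining modalities. How far the cited criteria would settle the matter cannot be judged from the documents.

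Three stronger readings are tempting and are not supported:

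- **The most favorable modality wins.** The and/or wording may only list the tests that apply to a given disease. It leaves a conflict unresolved; it does not say that a response on one modality outweighs progression on another.
- **A response on a second regimen after progression counts.** Section 3.2 is triggered by a standard-of-care biopsy and does not mention progression, while Section 11.1 takes progressing subjects off study therapy. Read together, these could place a later response outside treatment. However, progression is not among the off-study reasons in Section 11.2, and Section 3.2 applies during the study. How the sections interact, and which regimen a response belongs to, is therefore left open.
- **The inflation is largest in neuroblastoma.** Section 5 calls for MIBG/PET where indicated for the tumor type, and the same criteria cover PET in any stratum. No case mix is given.

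It is also fair to say that MIBG/PET complete response is naturally read as no positive lesion on the scan, so adding the condition there is only a clarification.

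**Conclusion.** The point holds as a gap in the response rules. As written, a single MIBG/PET scan can meet both partial response and progression, and nothing in the plan stops that subject from counting as an ORR responder while also being a PFS event with a zero-length response. The rules fail to prevent this; they do not direct it.

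The effect is confined to ORR, duration of response and the ORR comparison between the two cohorts. Both cohorts use the same definitions, so any error would cancel only if the frequency of such scans and their handling were alike in both, which the documents do not show. The primary feasibility endpoint is untouched, and no decision rule is attached to ORR, which Section 12.4 reports as rates with exact 95% confidence intervals.

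The existence of the overlap rests on no assumption beyond a literal reading of Section 7.3. Its size cannot be estimated from the documents. It is worth correcting before the analysis because the correction is simple and the alternative is case-by-case judgment on an outcome already seen.

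**What to change.** Keep the existing response thresholds and make three changes in Section 7.3, with the synopsis aligned:

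1. Add to MIBG/PET partial response that no new positive lesion may be present, and state the same for complete response for clarity.
2. Assign one overall status per time point across CT/MRI, MIBG/PET and marrow, with PD in any modality making that time point PD. The rule should also say what results when one modality shows a response and another is stable.
3. Derive best response from time points up to and including the first PD.

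Separately, Sections 3.2 and 11.1 must be reconciled on whether a subject can change regimen after progression. Which clinical rule applies is for the study team. For the analysis, any response on a changed regimen should be listed apart from ORR.

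The cost is a few sentences and a re-derivation from scans that Section 7.2 already requires to be sent to the NMTRC, together with the marrow results. No new procedures are needed. The downside is that the reported ORR may be slightly lower.
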